2	Advanced adenoma (AA), including: 
 2.1. Adenoma with carcinoma in situ or high-grade dysplasia, any size 2.2. Adenoma, villous growth pattern ($\geq 25\%$), any size 2.3. Adenoma ≥ 1.0 cm in size 2.4. Sessile serrated adenoma/polyp (SSA/P) with or without cytological dysplasia ≥ 1.0 cm and hyperplastic polyps (HP) ≥ 1.0 cm. 2.5. Traditional serrated adenoma (TSA), any size 	Advanced adenoma (AA), including: 
 2.1. Adenoma with carcinoma in situ or high-grade dysplasia, any size 2.2. Adenoma, villous growth pattern ($\geq 25\%$), any size 2.3. Adenoma ≥ 1.0 cm in size 2.4. Sessile serrated adenoma/polyp (SSA/P) with or without cytological dysplasia ≥ 1.0 cm 2.5. Traditional serrated adenoma (TSA), any size
3	Non-advanced adenoma (NAA)	Non-advanced adenoma (NAA)

This document contains confidential, proprietary information and may not be reproduced or disclosed in whole or in part without written authorization from Freenome Holdings, Inc

		Approval Status	Approved
		Effective Date	5-Jan-2024
Document Number	PL-00052	Current Revision	5
Document Title	Clinical Validation of Freenome's Methylation Blood Test for the Early Detection...		
Document Category	Plan		

[figure not shown]
Cat.	Definition for Central Pathology Review	Definition for Statistical Analysis
	3.1. ≥ 5 adenomas, all < 1.0 cm in size, non-advanced 3.2. 1 to <5 adenomas, all < 1.0 cm in size, non-advanced	3.1. ≥ 5 adenomas, all < 1.0 cm in size, non-advanced 3.2. 1 to <5 adenomas, all < 1.0 cm in size, non-advanced 3.3. HP ≥ 1.0 cm
4	Negative (NEG) 4.1. All SSA/P < 1.0 cm, and HP < 1.0 cm not in sigmoid or rectum 4.2. HP < 1.0 cm in the sigmoid or rectum 4.3. Negative upon histopathological review 4.4. No findings on colonoscopy, no histopathological review	Negative (NEG) 4.1. All SSA/P < 1.0 cm, and HP < 1.0 cm not in sigmoid or rectum 4.2. HP < 1.0 cm in the sigmoid or rectum 4.3. Negative upon histopathological review 4.4. No findings on colonoscopy, no histopathological review

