8.4. Subgroup Analyses

Note: PREEMPT is not prospectively powered for subgroup analysis, nor is study alpha controlled for subgroup analysis. Reported analyses and p-values should be interpreted accordingly.

For subjects in the FAS, the condition prevalence (i.e. CRC, AA, Non-ACN) and clinical performance (unless otherwise noted, CRC sensitivity, AA sensitivity, and non-ACN specificity) of FMBT-CRC will be compared using Fisher-Freeman-Halton Exact tests for the following categorical variables (FDA 2017):

- Biological sex
- Race/ethnicity
- Categorical age brackets (note: for this analysis, a Cochrane-Armitage test for trend will be performed)
- Smoking status
- CS completion within 90 days vs. > 90 but \leq 120 days after blood collection
- For CRC, cancer stage
- For CRC, location (proximal, distal and rectal)
- For AA, sub-type (2.1-2.5)
- For AA, location (proximal, distal and rectal)
- For AA, index lesion size (\leq 5, 6-9, 10-19, 20-29, and \geq 30mm). (note: for this analysis, a Cochrane-Armitage test for trend will be performed)

The clinical performance of FMBT-CRC will also be analyzed via multivariate logistic regression (probability of a positive FMBT-CRC result as a function of listed variables) as follows:

This document contains confidential, proprietary information and may not be reproduced or disclosed in whole or in part without written authorization from Freenome Holdings, Inc

		Approval Status	Approved
		Effective Date	5-Jan-2024
Document Number	PL-00052	Current Revision	5
Document Title	Clinical Validation of Freenome's Methylation Blood Test for the Early Detection...		
Document Category	Plan		

- For NAA and AA (Categories 2-3), analysis of test positivity by index lesion size and location. The model will be repeated to also include age, biological sex, and race variables.
- For non-ACN, analysis of test positivity controlling for race, biological sex, and age.
- For CRC and AA (separately), analysis of test positivity, controlling for age, biological sex, race, index lesion size and lesion location.

Note: for multivariate logistic regression, Wald tests will be used to evaluate each factor for statistical significance, and age will be treated as a continuous factor.

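### SAP 8.4 analyses advanced-adenoma detection by lesion size without histological subtype, although Table 3 ties the two together below 1.0 cm

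*SAP*

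**What the plan says.** SAP Section 8.4 lists variables across which test performance is compared. One entry begins "For AA, index lesion size" and gives five bins (≤5, 6-9, 10-19, 20-29 and ≥30 mm) with a Cochran-Armitage trend test. Subtype 2.1-2.5 is a separate entry with its own exact test. The section then specifies logistic models for test positivity, including: "For CRC and AA (separately), analysis of test positivity, controlling for age, biological sex, race, index lesion size and lesion location". Wald tests are to be reported for each factor. No analysis examines size within subtype or adjusted for it.

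Table 3 (Section 4.6, statistical-analysis definition) defines the AA subtypes:
- No size floor: "2.1. Adenoma with carcinoma in situ or high-grade dysplasia, any size"; 2.2, "Adenoma, villous growth pattern" (at least 25%, any size); and "2.5. Traditional serrated adenoma (TSA), any size".
- Floor of 1.0 cm: "2.3. Adenoma ≥ 1.0 cm in size"; and 2.4, "Sessile serrated adenoma/polyp (SSA/P) with or without cytological dysplasia ≥ 1.0 cm".

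Section 8.4 also states that subgroup analyses are neither powered nor alpha-controlled.

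**The concern.** Size and histology are linked by definition. The two bins below 10 mm consist entirely of high-grade, villous or traditional serrated lesions. The three larger bins also contain plain adenomas and sessile serrated lesions, which are advanced on size alone (2.3) or only once they reach that size (2.4). An unstratified trend compares groups with different histology.

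If the test picks up 2.1, 2.2 and 2.5 lesions more readily, the small bins look better than size alone would make them. A test with no size dependence could then appear to detect small lesions best, and a true rise with size could be weakened. The separate subtype comparison does not resolve this, because it does not hold size fixed. What is at stake is how the reported size trend, and the size coefficient in the AA model, are read.

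**Working it through.** **1. The plan's own figure.** The documents state no figure for the size trend. The nearest is the AA sensitivity calculation in SAP 7.5, 250 positive of 1,929. Wilson lower bound = [p + z²/2n − z√(p(1−p)/n + z²/4n²)] / (1 + z²/n), with p = 250/1,929 = 0.1296 and z = 1.96:
(0.1296 + 0.0010 − 0.0150) / 1.0020 = 0.1153. This reproduces the stated 11.53%.

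**2. Composition of the bins, from Table 3.**

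| Size bins | 2.1 / 2.2 / 2.5 | 2.3 / 2.4 |
|---|---|---|
| ≤5 and 6-9 mm | possible | impossible |
| 10-19, 20-29, ≥30 mm | possible | possible |

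This step needs no assumption. It also shows that size and subtype are not fully collinear, since the first group occurs at every size.

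**3. Number of AA.** SAP Section 7 gives AA prevalence as beta(34.265, 436.699) and an FAS of 19,000. Mean prevalence = 34.265/(34.265 + 436.699) = 7.28%. Unrounded, 0.072755 × 19,000 = 1,382. The 1,929 of SAP 7.5 serves as an upper case.

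**4. Assumptions not in the documents.**
- Sensitivity 20-25% in 2.1/2.2/2.5 and 12% in 2.3/2.4. The odds ratio is (0.20/0.80)/(0.12/0.88) = 1.8 to (0.25/0.75)/(0.12/0.88) = 2.4.
- 5-15% of AA under 10 mm, split 30/70 over the two small bins.
- AA of 10 mm or more split 70/20/10 over the three large bins, with 20% of them 2.1/2.2/2.5.

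**5. Expected sensitivity with no size effect within histology.**
Under 10 mm: 20-25%.
10 mm or more: 0.20 × 20% + 0.80 × 12% = 13.6%, up to 0.20 × 25% + 0.80 × 12% = 14.6%.
The crude trend therefore points downward although size does nothing.

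**6. Simulated trend tests** (equally spaced scores, two-sided 0.05; the stratified version sums score and variance over the two histology groups), 1,382 AA:

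| True situation | Planned five-bin trend | Stratified trend |
|---|---|---|
| No size effect: significant inverse trend | 12-72% | about 2-3% |
| Gradient continuing below 10 mm (relative sensitivity 0.56/0.70/0.9/1.15/1.4): upward trend detected | 26-56% | 77-89% |
| Same gradient: significant inverse trend | about 0.1% or less | – |

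With 1,929 AA and no size effect, the false inverse rate rises to 14-84%, so more data make it worse.

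If the gradient applies only from 10 mm upward, the planned test does less well. It detects the gradient in 2-35% when lesions under 10 mm have relative sensitivity 0.9, and in 0.5-28% when they have 1.0.

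**7. A second set of assumptions.** Take 1,929 AA, overall sensitivity 14.0%, 10% of AA under 10 mm, 20/25/30% being 2.1/2.2/2.5 in the three large bins, and a true odds ratio of 1.2 per size step. Detection, planned versus stratified, is 64% versus 63% with no histology effect, 23% versus 66% at a histology odds ratio of 2, and 8% versus 68% at 3. The loss comes from the histology effect and vanishes without it.

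Only the trend test was simulated. The SAP does not say how size enters the logistic model, so for that model the argument is structural and carries no figure.

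**The case against.** Several counter-arguments have force.

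- **No endpoint depends on it.** No objective or acceptance criterion concerns lesion size, and Section 8.4 tells the reader how to treat its p-values. This stands and limits the severity. The warning concerns power and multiplicity, however, and does not address bias.
- **Sensitivity by size bin is a valid description of AA as defined, case mix included.** True, and the bins should still be shown. A single trend p-value, or a size coefficient described as controlled for other factors, invites reading as an effect of size.
- **Much is already visible.** Subtype has its own comparison, and Section 8.1 provides counts, percentages and Wilson intervals by category. A gradient among the large bins could be seen there. Neither display separates size from subtype.
- **The size of the effect is assumed.** This stands. The documents give neither sensitivity by subtype nor the share of AA under 10 mm.

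A reader might infer that a real size gradient would be reversed or almost entirely hidden. The documents do not support that. Very low detection arises when the gradient is taken to stop at 10 mm. When it continues downward, significant reversal occurs in about 0.1% of cohorts or fewer under the main assumptions. In the second set, reversal needed about 20% of AA under 10 mm and a histology odds ratio of 3-4 (12% and 36% of cohorts respectively).

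A reader might also extend the point to the other models. The quoted sentence covers CRC as well, where this definitional link does not exist. In the pooled NAA and AA model, adding lesion category would adjust for a variable partly defined by the 10 mm cut (2.3 versus 3.1 and 3.2) and could absorb the step being studied.

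**Conclusion.** The point holds, as a minor one. It is certain from the SAP that the AA size trend and the AA logistic model leave out subtype, and that Table 3 restricts AA under 1.0 cm to 2.1, 2.2 and 2.5. The consequence is conditional on those histologies testing positive more often. Under the assumptions in steps 3 and 4, the planned trend gives a false inverse result in about 12-72% of cohorts when size has no effect. Its detection of a real, continuing gradient is about 26-56%, against 77-89% with stratification, and lower if the gradient stops at 10 mm. If subtype does not affect positivity, there is no bias.

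The effect is confined to interpreting a subgroup analysis without alpha control. No primary or secondary endpoint changes, and the overall AA sensitivity estimate is untouched.

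**What to change.** In SAP 8.4:
1. Add AA subtype to the AA logistic model, either as 2.1-2.5 (up to four parameters) or grouped as 2.1/2.2/2.5 versus 2.3/2.4. State how size enters the model.
2. Run the AA size trend stratified by that grouping, with the trend within the bins of 10 mm and larger as support.
3. Keep sensitivity by all five size bins as a descriptive display.
4. Leave the CRC model as it is, and do not add lesion category to the pooled NAA and AA model.

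The cost is SAP wording and a few parameters. Subtype is already recorded for the planned subtype comparison, and the critical value in SAP 7.5 implies about 250 positive AA if that criterion is just met at 1,929 AA. The statistical price is a small power loss if histology has no effect, at most about 6 percentage points for the stratified trend in the scenarios above. Restricting the trend to 10 mm and larger would cost more (87% to 70% in one run at 1,929 AA with no histology effect), so that analysis should be supportive only. Information on size below 10 mm will come only from 2.1, 2.2 and 2.5 lesions, and the report should say so.

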8.5. Additional Analyses

1. Descriptive statistics for medical history, concomitant medication, adverse events, summary of blood test accessioning, processing, and findings, and summary of colonoscopy findings.
2. Diagnostic yield.
3. Report percentage of results with invalid tests.
4. Subject demographics and analysis of test performance (Sn, Sp, PPV, NPV, PLR and NLR) homogeneity by sites stratified by Science 37 and non-Science 37 sites, and US vs non-US sites.
5. Analysis of test performance (Sn, Sp, PPV, NPV, PLR and NLR) for the following age-based USPSTF (2021) Grade groups:
 - 5.1. USPSTF Grade "A" (50-75)
 - 5.2. USPSTF Grade "A+C" (50-85)
 - 5.3. USPSTF Grade "B+A" (45-75)
 - 5.4. USPSTF Grade "B+A+C" (45-85)
6. Comparison of age and sex distributions to US estimates.
7. NPV and PPV using U.S. IUP prevalence.

This document contains confidential, proprietary information and may not be reproduced or disclosed in whole or in part without written authorization from Freenome Holdings, Inc

		Approval Status	Approved
		Effective Date	5-Jan-2024
Document Number	PL-00052	Current Revision	5
Document Title	Clinical Validation of Freenome's Methylation Blood Test for the Early Detection...		
Document Category	Plan		

8. Direct rate standardization will be used to project the sensitivity (Sn_{ACN} , Sn_{CRC} , and Sn_{AA}) and specificity ($Sp_{non-ACN}$) of FMBT-CRC to the general population based on age brackets and biological sex. Standardization will be repeated, projecting for condition prevalence (based on age brackets and sex) to the general population, prior to projecting the sensitivity and specificity to the general population.
9. Number needed to screen per disease-positive finding (CRC, Stage I to III CRC, AA).
10. Benefit-harm analysis: sensitivity, specificity, PPV, NPV, and likelihood ratios have limited utility for guiding clinical decision-making and don't convey the impact of clinical application (Evans 2016). Additionally, actuarial-based frameworks such as BED-FRAME, that are designed to assess clinical impact, are not able to incorporate the dynamic relationship between natural history (i.e. the adenoma-carcinoma sequence) and guideline-based screening and colonoscopy surveillance. Because of these limitations, FMBT-CRC performance characteristics will be used in conjunction with a validated microsimulation model to assess lifetime comparative tradeoffs in harms (e.g. colonoscopy adverse events), burden (e.g. total colonoscopies), and benefit (e.g. life-years-gained), utilizing the same systematic approach to evaluate benefit-risk trade-offs as the United States Preventive Services Task Force (USPSTF) and Cancer Intervention and Surveillance Modeling Network (CISNET).

This document contains confidential, proprietary information and may not be reproduced or disclosed in whole or in part without written authorization from Freenome Holdings, Inc

		Approval Status	Approved
		Effective Date	5-Jan-2024
Document Number	PL-00052	Current Revision	5
Document Title	Clinical Validation of Freenome's Methylation Blood Test for the Early Detection...		
Document Category	Plan		

8.7. Demographics for Evaluated vs. Unevaluated Subjects

Subjects included in the EN set may be excluded from FAS for various reasons. Additionally, subjects enrolling prior to April 5, 2021 are not included in either the EN or the FAS. The distribution of categorical demographic variables (stratified age, race/ethnicity, etc.) will be descriptively compared to the corresponding distribution from the FAS set for the following:

- Enrolled subjects prior to April 5, 2021 (date used to define the EN and FAS set)
- Subjects included in EN with missing or incomplete CS results
- Subjects included in EN with missing FMBT-CRC results

Subject Accounting

There will be a detailed accounting of every subject in the EN cohort, noting their inclusion in FAS or the reason(s) for their exclusion from FAS.

8.8. Statistical Software

All tables, listings and figures will be primarily produced using SAS® Version 9.3 or later (SAS Institute, Cary, NC) and R version 4.2 or later (R Foundation for Statistical Computing, Vienna, Austria).

9. QA/QC and Data Handling

All data collection and monitoring methods are included within the Protocol Version 3, dated 09 April 2021.

Document Revision History

Table 7 - Revision History

Rev	Change	Author
1.0	Initial release	[REDACTED]

This document contains confidential, proprietary information and may not be reproduced or disclosed in whole or in part without written authorization from Freenome Holdings, Inc

		Approval Status	Approved
		Effective Date	5-Jan-2024
Document Number	PL-00052	Current Revision	5
Document Title	Clinical Validation of Freenome's Methylation Blood Test for the Early Detection...		
Document Category	Plan		

2.0	See Table 8	[REDACTED]
3.0	See Table 9	[REDACTED]
4.0	See Table 10	[REDACTED]
5.0	See Table 11	[REDACTED]

Table 8 - PL-00052 Rev 2 Summary of Changes

Rev 2 Section #	Change
Synopsis	Updated to add a brief statement that test results will be determined on two separate classification models.
Study Objectives	Updated to include PPV (for ACN) and NPV (for Non-ACN) as primary objectives per FDA feedback in [REDACTED]. Included Fixed Sequence Tiered approach to Endpoint evaluation.
Section 1.1 Background	Updated to describe USPSTF recommendation of 1-3 year screening interval for screening modalities similar to FMBT-CRC. Updated to note that for purposes of statistical analysis, the definition of AA is changed to remove hyperplastic polyps ≥ 1.0 cm from AA category as per FDA feedback in [REDACTED].
Section 2 Device Description	Updated the device description for clarity regarding the FMBT-CRC Methylation assay.
Section 2.2 Subsystem Controls and Calibrators	Renamed section to "Subsystem Controls" because calibrators applied to the [REDACTED] subsystem, which is no longer applicable.
Section 2.4 FMBT-CRC-Multiomics Software Platform	Updated to describe classifier workflow with two separate models.
Section 3.1 Detection of ACN	[REDACTED]

This document contains confidential, proprietary information and may not be reproduced or disclosed in whole or in part without written authorization from Freenome Holdings, Inc

		Approval Status	Approved
		Effective Date	5-Jan-2024
Document Number	PL-00052	Current Revision	5
Document Title	Clinical Validation of Freenome's Methylation Blood Test for the Early Detection...		
Document Category	Plan		

Rev 2 Section #	Change
	[REDACTED]
Section 3.5 Classification	Updated to include classification model calculation for FMBT-CRC-Methylation model.
Section 4.4 Colonoscopy	Updated to include rationale for accepting patient samples that had CS within 90-120 days of blood collection.
Section 4.5 Study Duration	Removed in Rev 2 as this was repeat information from Section 4.4 Colonoscopy. All Section 4 sub-sections after 4.4 have been renumbered in SAP Rev 2.
Section 4.6 Central Pathology Review	Note that the central pathology review described has already occurred using classification previously provided. Freenome cannot change this section. Table 6 updated to differentiate hyperplastic polyps ≥ 1.0 cm from sessile serrated adenoma/polyp ≥ 1.0 cm by moving hyperplastic polyps ≥ 1.0 cm to a new NAA sub-category (3.3) for the purposes of the statistical analysis. These changes were intended to reflect FDA feedback to [REDACTED]
Section 4.7 Subject Disposition	Updated the subject disposition flowchart to better demonstrate subjects' disposition to different analysis sets and distinguish the exclusion reasons by blood sample issues versus colonoscopy/histopathology diagnosis issues.
Section 4.8 Protocol Deviations	Updated to clarify that deviation is from protocol defined procedure. Removed "visit not done" as a deviation as it is a duplicate to the "protocol-defined procedure".
Section 4.9 Blinding	Updated blinding definition to include blood test results that could bias the study.
Section 5.3 Safety Analysis Set	Updated the definition of Safety Analysis Set (SAS) to ensure subjects who had attempted blood collection are included for the adverse event analysis

This document contains confidential, proprietary information and may not be reproduced or disclosed in whole or in part without written authorization from Freenome Holdings, Inc

		Approval Status	Approved
		Effective Date	5-Jan-2024
Document Number	PL-00052	Current Revision	5
Document Title	Clinical Validation of Freenome's Methylation Blood Test for the Early Detection...		
Document Category	Plan		

Rev 2 Section #	Change
Section 6.1 Tiered Endpoints Families	New section added to describe Tiered Endpoint Families for FMBT-CRC Multiomics and Methylation Models as separate.
Section 6.2 Diagnostic Accuracy Estimation and Notation	Updated to replace Clopper-Pearson method with Wilson score method for analysis per FDA feedback in [REDACTED]
Section 6.3 Study Objectives	Updated to include PPV (for ACN) and NPV (for Non-ACN) as primary objectives per FDA feedback in [REDACTED] Updated to include Tiered Endpoint Family approach for the primary objectives.
Section 6.4 Study Hypotheses	Updated to describe two tiered analysis approach for FMBT-CRC Multiomics and Methylation models. Updated to move hypotheses for non-ACN NPV and ACN PPV from Secondary Objectives to Primary Objectives.
Section 6.5 Study Endpoints	Updated to replace Clopper-Pearson method with Wilson score method for analysis per FDA feedback in [REDACTED] Updated to include NPV for non-ACN and PPV for ACN as primary objectives per FDA feedback in [REDACTED]
Section 7 Sample Size Justification	Updated to replace Clopper-Pearson method with Wilson score method for analysis per FDA feedback in [REDACTED]
Section 7.1 CRC Sensitivity Sample size Justification	Updated to CI lower bounds corresponding to 38/48 as 65.74% instead of 65.01%. These values were updated based on feedback in [REDACTED]
Section 7.2 Non-ACN Specificity Sample Size Justification	Updated to CI lower bounds corresponding to 403/456 as 85.11% instead of 85.07%. These values were updated based on feedback in [REDACTED]
Section 7.5 AA Sensitivity Sample	Updated to CI lower bounds corresponding to 21/131 is 10.73% instead of 10.21% These values were updated based on feedback

This document contains confidential, proprietary information and may not be reproduced or disclosed in whole or in part without written authorization from Freenome Holdings, Inc

		Approval Status	Approved
		Effective Date	5-Jan-2024
Document Number	PL-00052	Current Revision	5
Document Title	Clinical Validation of Freenome's Methylation Blood Test for the Early Detection...		
Document Category	Plan		

Rev 2 Section #	Change
size Justification	in [REDACTED]
Section 8.1 General Considerations Impacting the Data Analysis	Updated to replace Clopper-Pearson method with Wilson score method for analysis per FDA feedback in [REDACTED] Removed NEG 4.4 Category.
Section 8.2 P Values and Confidence Interval	Updated to replace Clopper-Pearson method with Wilson score method for analysis per FDA feedback in [REDACTED] Updated to describe the two tiered endpoint family analysis approach.
Section 8.4 Subgroup Analysis	Updated to clarify the method used for statistical significance, specified that age will be treated as a continuous factor, and removed a redundant model

Table 9 - PL-00052 Rev 3 Summary of Changes

Rev 3 Section #	Change
Title	In title, replaced "Multiomics" with "Methylation"
List of Abbreviations and Definitions	Updated FMBT-CRC to FMBT-CRC/FMBT-CRC Methylation for clarity.
List of Abbreviations and Definitions	Added a definition for Enrolled* subjects. Added a definition for Index Lesion.
List of Abbreviations and Definitions	Updated the definition of FRNM-SP for clarity.
Synopsis Study Design	Deleted reference to "two separate classification models" and references to a "multiomics" test. Deleted reference to "tiered endpoint family". Deleted the section "Fixed Sequence (Serial Gatekeeping) Tiered Approach to Endpoint Evaluation." Deleted Figure 1, which described Fixed Sequence (Serial Gatekeeping) approach.

This document contains confidential, proprietary information and may not be reproduced or disclosed in whole or in part without written authorization from Freenome Holdings, Inc

		Approval Status	Approved
		Effective Date	5-Jan-2024
Document Number	PL-00052	Current Revision	5
Document Title	Clinical Validation of Freenome's Methylation Blood Test for the Early Detection...		
Document Category	Plan		

Rev 3 Section #	Change
Section 1.1 Background	Added text to describe the reason for re-classifying Category 2.4 hyperplastic polyps was due to FDA feedback.
Section 2 Device Description	Deleted reference to "multiomics", ' [REDACTED]', and ' [REDACTED]' subsystem.
Section 2 Device Description	Added FMBT Blood Collection Kit and FMBT Pre-Analytical Subsystem to the list for the overall test system.
Figure 1	Updated figure to remove [REDACTED] assay.
Figure 2	Updated to remove ' [REDACTED] assay.'
Section 2.2 [REDACTED] subsystem	Deleted section, as it refers to the [REDACTED] subsystem.
Table 2	Deleted, since it applies to the [REDACTED] subsystem.
Table 3	Deleted, since it applies to the [REDACTED] subsystem.
Table 5	Deleted, since it applies to the [REDACTED] subsystem.
Section 2.4 FMBT-CRC-Multiomics	Deleted, since multiomics will not be tested with this Plan.
Figure 3	Deleted, since it applies to multiomics, and multiomics will not be tested with this Plan.
Figure 4	Deleted, since it applies to multiomics, and multiomics will not be tested with this Plan.
Section 2.5 FMBT-CRC—Methylation Software Platform	Changed the section title to "FRNM Software Platform (SP" to align with correct nomenclature. Updated this section to align with actual device description and to make language more clear for FMBT-CRC-Methylation, given deletions in section 2.4.
Section 3.1 Detection of ACN	Deleted reference to FMBT-CRC Multiomics Classification Model. Updated verbiage pertaining to FMBT-CRC Methylation Classification Model.
Section 3.2 CpG	Updated entire section describing how CpG Methylation Score is

This document contains confidential, proprietary information and may not be reproduced or disclosed in whole or in part without written authorization from Freenome Holdings, Inc

		Approval Status	Approved
		Effective Date	5-Jan-2024
Document Number	PL-00052	Current Revision	5
Document Title	Clinical Validation of Freenome's Methylation Blood Test for the Early Detection...		
Document Category	Plan		

Rev 3 Section #	Change
Methylation Score	derived by providing more specifics of the process.
Section 3.3 [REDACTED] [REDACTED]	Section deleted, since it applies to [REDACTED] score.
Section 3.3 Model ensemble	Added a Model ensemble section to describe the training, tuning, and testing procedure for FMBT-CRC-Methylation model.
Section 3.4 Integrating Methylation and [REDACTED] Score into FMBT-CRC-Multiomics System Level Score	Section deleted, as it applies to integrating Methylation and [REDACTED] Subsystems.
Section 3.5 Classification (now Section 3.4)	Section updated to only apply to Methylation classification. Provided updated language and symbols for comparing Score to Cutoff.
Section 4 Scope of the Analysis	Improved the grammar and readability of the section. Removed redundant verbiage.
Section 4 Scope of the Analysis	Clarified enrollment cutoff date to read "on or after April 5 th " or "April 5 th 2021 (inclusive) cutoff" so language aligns with existing section 7.12 language that defines exclusions as prior to April 5 th .
Section 4.4 Colonoscopy	Updated language to make it clear the adjectives "poor" and "inadequate" applied to bowel preparation.
Section 4.6 Central Pathology Review	Added description of index lesion.
Section 4.7 Subject Disposition Figure 7 and bullet points below	Updated definition of "All Enrolled" subjects to include any subject enrolled in PREEMPT. Introduced "Enrolled*" term to delineate from subjects enrolled prior to April 5 th , 2021. Changed "blood sample not obtained" to "blood sample not available" Changed order of bullet points of "Death" and "Adverse Event" Changed "Unevaluable colonoscopy result" to "Unevaluable colonoscopy result for non-ACN subjects". Removed "Occult IBD found on colonoscopy" from "Subjects"

This document contains confidential, proprietary information and may not be reproduced or disclosed in whole or in part without written authorization from Freenome Holdings, Inc

		Approval Status	Approved
		Effective Date	5-Jan-2024
Document Number	PL-00052	Current Revision	5
Document Title	Clinical Validation of Freenome's Methylation Blood Test for the Early Detection...		
Document Category	Plan		

Rev 3 Section #	Change
	excluded due to colonoscopy or histopathology results" as these subjects could be considered part of IUP. Updated footer to "on or after April 5 th , 2021" to define *Enrolled subjects and added a footer about the SAS group.
Section 4.7 Subject Disposition	Clarified protocol deviation and blood sample failure language.
Section 4.8 Protocol Deviations	Updated protocol deviations section to align with Tables, Listings, and Figures
Section 4.9 Blinding	Added document number for Sponsor's blinding plan.
Section 5 Analysis Populations	Added Enrolled* population and clarified enrollment cutoff date to read "on or after April 5 th " so language aligns with existing section 7.12 language that defines exclusions as prior to April 5 th .
Section 6.1 Tiered Endpoint Families	Deleted this section, since two models will not be evaluated with this Plan.
Section 6.2 Diagnostic Accuracy Estimation and Notation	Corrected the calculations for PLR_CRC, PLR_AA, NLR_CRC, and NLR_AA so when they are used with corresponding prevalences, the resulting PPV and NPVs will align with outcomes of the formulas.
Section 6.2 Diagnostic Accuracy Estimation and Notation	Aligned the PLR, NLR, PPV, and NPV confidence interval approach to the Score method, per FDA (2017) guidance.
Section 6.3 Study Objectives	Replace "positive predictive value" with "PPV" to make the bullet point more consistent with its NPV counterpart.
Section 6.4 Study Hypotheses	Deleted reference to evaluating two tiers of endpoint families, since two models will not be evaluated.
Section 6.4 Study Hypotheses	Removed hypothesis-testing language and replaced with acceptance criteria language. Updated powering and sample size estimates based on performance assumptions and simulation-based approach for predictive values. Predictive value (NPV and PPV) endpoints now based on delta compared to observed

This document contains confidential, proprietary information and may not be reproduced or disclosed in whole or in part without written authorization from Freenome Holdings, Inc

		Approval Status	Approved
		Effective Date	5-Jan-2024
Document Number	PL-00052	Current Revision	5
Document Title	Clinical Validation of Freenome's Methylation Blood Test for the Early Detection...		
Document Category	Plan		

Rev 3 Section #	Change
	prevalence (for non-ACN and ACN, respectively).
Section 7 Sample Size Justification	Updated Sample Size Justification section to align with Section 6.
Section 7.1 CRC Sensitivity Sample Size Justification	Updated sample size requirements with new assumptions. Added Score confidence interval language.
Section 8.1 General Considerations Impacting the Data Analysis	Updated the quantile values that will be summarized for continuous variables.
Section 8.2 P values and Confidence Intervals	Deleted reference to two tiers of endpoint families.
Section 8.3 Baseline Subject Characteristics	Added “EN” analysis set. Removed “family history” from baseline subject characteristics, since family history of CRC is a study exclusion criteria. Added BMI and lifestyle information to baseline subject characteristics.
Section 8.4 Subgroup Analyses	Added a disclaimer about interpretability of subgroup analyses and added specifics about the statistical tests that will be performed. Added reference to FDA’s guidance for subgroup evaluation for Medical Devices. Clarified that Fisher-Freeman-Halton Exact test and Cochrane-Armitage test for trend will be used for subgroup evaluation.
Section 8.5 Ad-hoc analyses	Changed title of section to “Exploratory analyses”
Section 8.5 Ad-hoc analyses	Added verbiage in the direct standardization section to align with commitments made to FDA.
Section 8.5 Ad-hoc analyses	Added an ad-hoc analysis for quantifying lifetime burdens and benefits, using methods that are similar to USPSTF/CISNET. Added Evens 2017 reference.

This document contains confidential, proprietary information and may not be reproduced or disclosed in whole or in part without written authorization from Freenome Holdings, Inc

		Approval Status	Approved
		Effective Date	5-Jan-2024
Document Number	PL-00052	Current Revision	5
Document Title	Clinical Validation of Freenome's Methylation Blood Test for the Early Detection...		
Document Category	Plan		

Rev 3 Section #	Change
Section 8.5 Ad-hoc analyses	Updated the order of ad-hoc analyses for readability.
Section 8.5 Ad-hoc analyses	Updated verbiage of "maximum polyp size" to "index lesion size" for clarity.
[REDACTED]	[REDACTED]
Section 8.7 Demographics vs Unevaluated Subjects	Changed "ALL" to "EN" to reflect the correct analysis set for these analyses.

This document contains confidential, proprietary information and may not be reproduced or disclosed in whole or in part without written authorization from Freenome Holdings, Inc

		Approval Status	Approved
		Effective Date	5-Jan-2024
Document Number	PL-00052	Current Revision	5
Document Title	Clinical Validation of Freenome's Methylation Blood Test for the Early Detection...		
Document Category	Plan		

Table 10 - PL-00052 Rev 4 Summary of Changes

Rev 4 Section #	Change
Section 6.3 Study Acceptance Criteria	Updated specificity acceptance criterion to 85.0% (from 89.0%) Updated non-ACN NPV acceptance criterion to 0.16% (from 0.26%) Updated ACN PPV acceptance criterion to 1.17% (from 2.19%)
Section 6.4 Study Endpoints	Updated specificity acceptance criterion to 85.0% (from 89.0%) Updated non-ACN NPV acceptance criterion to 0.16% (from 0.26%) Updated ACN PPV acceptance criterion to 1.17% (from 2.19%)
Section 7.2 Non-ACN Specificity Sample Size Justification	Updated specificity acceptance criterion to 85.0%. Updated corresponding sample size to 454. Updated associated critical value to 401/454.
Section 7.3 Non-ACN Negative Predictive Value Sample Size Justification	Updated non-ACN NPV acceptance criterion to 0.16% (from 0.26%)
Section 7.4 ACN Positive Predictive Value Sample Size Justification	Updated ACN PPV acceptance criterion to 1.17% (from 2.19%)
Section 8.5 Exploratory Analysis	Section was renamed to Additional Analyses
Section 8.5 Exploratory Analysis	Added exploratory analysis for test performance by age-based USPSTF (2021) Grade groups.

